### **3 STUDY OBJECTIVE(S) AND DESIGN**

#### **3.1 Study Objective(s)**

The main objective of this study is to evaluate the efficacy of ASP015K (100 and 150 mg/day) versus placebo administered in combination with MTX in RA patients who had an inadequate response to MTX. The primary efficacy variables are the ACR20 response rate at Week 12 and suppression of joint destruction (change from baseline in mTSS) at Week 28. This study will also investigate pharmacokinetic, pharmacodynamic, and safety profiles. Furthermore, this study will examine the long-term efficacy and safety (52 weeks).

#### **3.2 Study Design**

This study is a multi-center, randomized, placebo-controlled, double-blind, parallel-group, confirmatory study to evaluate the efficacy and safety of ASP015K (100 and 150 mg/day) administered in combination with MTX in patients with RA who had an inadequate response to MTX. The geographical scope of this study will be confined to Japan. MTX response is evaluated at the initiation of screening and then after the screening period, subjects will be randomly assigned at a 1:1:1 ratio to receive ASP015K 100 mg, ASP015K 150 mg, or placebo QD in combination with MTX. Subjects will orally receive the study drug after breakfast for 52 weeks. The target number of subjects is 170 patients per group.

Re-screening is allowed only in situations in which a subject underwent the screening procedures (i.e., scans and laboratory work) and owing to logistical circumstances, the allocated time window for these tests has expired. Re-screening is not permitted in cases in which the initial test results do not support eligibility based on inclusion and exclusion criteria. The subject must be classified as a screening failure at that time point.

Based on the consideration of the ethical issues related to long-term placebo use, inadequate responders in the placebo group, as determined by < 20% improvement from baseline in tender or painful joint count (TJC) and swollen joint count (SJC), will be switched at Week 12 to either ASP015K 100 mg or ASP015K 150 mg, and the dosage will be maintained until the end of treatment. In addition, subjects receiving placebo at Week 28 will be switched to either ASP015K 100 mg or ASP015K 150 mg, and the dosage will be maintained until the end of treatment. The ASP015K dose that will be started for placebo group subjects at Week 12 or Week 28 (100 or 150 mg) will be randomly chosen at baseline. The dose will be switched under the blinded condition.

Subjects who complete this study will be eligible for participation in the open-label extension study (015K-CL-RAJ2). Subjects will make a follow-up visit after the Week 52 visit if they do not enroll into the extension study on the day of the Week 52 visit.

Safety data obtained from this study will be reviewed by the Independent Data and Safety Monitoring Board (DSMB), which will make recommendations on study continuation, termination, or protocol revision from the safety perspective.

### 3.3 Randomization

The person responsible for assigning study drugs will randomly assign the study drugs and retain the treatment code under secrecy until the breaking of the treatment code.

The Case Registration Center will assign subjects who have been found to be eligible for enrollment in accordance with the case registration procedures to 1 of the following groups: ASP015K 100 mg, ASP015K 150 mg, or placebo groups at baseline in 1:1:1 ratio. At Week 12, subjects in the placebo group whose tender and swollen joint counts have not improved by 20% from baseline will be assessed as having an inadequate response, and they will be switched to receive either ASP015K at a dose of 100 mg or ASP015K at a dose of 150 mg. Subjects who are continuing to receive placebo at Week 28 will be switched to receive either ASP015K at a dose of 100 mg or ASP015K at a dose of 150 mg.

The dose of ASP015K (100 mg or 150 mg) to be administered to the placebo group from Week 12 or Week 28 is decided randomly at baseline, and study drugs must always be switched under double-blind conditions.

All drug numbers are assigned randomly by the Case Registration Center under blind conditions.

## 4 SAMPLE SIZE

A total of 510 treated patients, with 170 in each treatment group

[Rationale for the sample size]

The sample size calculation was based on ASP015K Japanese Phase IIb study (015K-CL-RAJ1) result and other Japanese studies for patients with RA [XELJANZ®, tablet, 5 mg, CTD (2013)] [CIMZIA, sc, 200 mg, Syringe, CTD (2012)]. In the 015K-CL-RAJ1 study, the primary efficacy endpoint, which was Percentage of Subjects achieving ACR20 response at Week 12/ET, was 54.5% in the 100 mg, and 65.5% in the 150 mg. Therefore, in the 015K-CL-RAJ4 study, it can be assumed to achieve same magnitude of ACR20 response at Week 12/ET for both 100 mg and 150 mg. For ACR20 response at Week 12/ET in the placebo group, it was assumed 25% based on other Japanese drugs for RA.

Meanwhile, the change in mTSS at Week 28 was estimated to be 0.5 in ASP015K 150 mg group, considering the results of the Japanese subgroup analysis of the Oral Scan Study of Tofacitinib, a drug of same class and indication (5 mg group: -0.0, 10 mg group: 0.5), Study CDP870-041 of Cimzia (100 mg group: 1.05, 200 mg group: 0.21, 400 mg group: 0.65), and Study RA0006 (200 mg group: 0.44). Similarly, the change in mTSS at Week 28 was estimated to be 2.0 in the placebo group, considering the results of the Japanese subgroup analysis of the Oral Scan Study (placebo group: 1.4), Study CDP870-041 (placebo group: 2.78), and Study RA0006 (placebo group: 2.49). The standard deviation of the change was also estimated and set to 4.0 based on the results reported from the same studies [Japanese subgroup analysis of the Oral Scan Study (placebo group: 3.15, 5 mg group: 1.09, 10 mg

group: 1.54), Study CDP870-041 (placebo group: 5.15, 100 mg group: 2.85, 200 mg group: 2.01, 400 mg group: 2.95), and Study RA0006 (placebo group: 5.52, 200 mg group: 1.83)].

On this assumption, the necessary sample size was calculated to enable to analyze ACR20 using the Fisher's exact test and the change in mTSS at Week 28 using the t-test. When a closed testing procedure (in Section 7.4.1.1 Primary Analysis) considering multiplicity is used in the primary analysis, the sample size needed to verify the hypotheses Step 1 through Step 3 at a 2-sided 5% significance level with 90% power is 151 subjects per group. By considering about 10% drop-out, this study will enroll 170 patients in each treatment group. Moreover, from the long term safety point of view, this sample size is also needed to keep 300 subjects for 6 month period, 100 subjects for 1 year period in both ASP015K 100 mg and 150 mg among RAJ2/RAJ3/RAJ4 studies.

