Moreover, taking note of the “Guidelines on methodology for clinical assessment of antirheumatic drugs” (PFSB/ELD Notification No. 0217001, dated 17 February 2006), the duration of treatment was set at 52 weeks to evaluate the 1-year efficacy and safety as secondary endpoints.

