### 6.5 Other Variables

- Duration of RA (years), calculated as: (Date of Baseline mTSS taken – Onset Date of RA +1) / 365.25, and then rounded to one decimal place. The onset date of RA doesn't have the day (e.g., 2013-03), therefore the first day of the month will be used (2013-03-01).  
\*: Missing onset date of RA will be imputed. For example, if month is missing (e.g., 2013), then the first day of January will be used (2013-01-01).

- Age at onset of RA (years), calculated as: (date of onset of RA – date of birth +1) / 365.25. Onset Date of RA will be handled in the same way as described above.
- Duration of exposure (days)  
Duration of exposure will be calculated in days, using the following formula:  
(‘Date of Last Dose of Study Drug’\* - ‘Date of First Dose of Study Drug’\*\* ) + 1  
\* = Max(EX1ENDT, EX2ENDT, EX3ENDT) [Study Drug and Reference Drug Dosing-page of the CRF]  
\*\* = EX1STDT [Study Drug Dosing -page of the CRF]
- Overall treatment compliance (during overall treatment period)

In the study, the subjects will be instructed to take 2 tablets once per day, totaling a daily dose of study dose. Therefore, overall treatment compliance will be based on number of tablets and calculated as follows:

$$\text{Treatment compliance (\%)} = \frac{\text{[Total number of tablets actually received in the treatment period]}}{\text{[Total number of tablets planned to receive in the treatment period]}} \times 100$$

where total number of tablets planned to receive in the treatment period = 2 × number of days the subject was in the treatment period (the previous date of Week 52 visit [for completed subjects] / date of withdrawal date [for discontinued subjects] – date of initial dose of study drug +1), and total number of tablets actually received in the treatment period will be calculated as:

(total number of tablets dispensed) – (total number of tablets returned) – (total number of tablets lost).

- Treatment compliance during the 12 weeks of study (up to Weeks 12)  
Treatment compliance (%) =

$$\frac{\text{[Total number of tablets actually received up to Weeks 12]}}{\text{[Total number of tablets planned to receive up to Weeks 12]}} \times 100$$

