where total number of tablets planned to receive up to Weeks 12 = 2 × number of days the subject was during 12 weeks (the previous date of Weeks 12 visit date [for completed Week 12 subjects] / date of withdrawal date [for discontinued before Week 12 subjects] – date of initial dose of study drug +1), and total number of tablets actually received up to Weeks 12 will be calculated as:

(total number of tablets dispensed up to Weeks 12) – (total number of tablets returned up to Weeks 12) – (total number of tablets lost up to Weeks 12).

- Treatment compliance during the 28 weeks of study (up to Weeks 28)  
Treatment compliance (%) =

$$\frac{[\text{Total number of tablets actually received up to Weeks 28}]}{\text{-----} \times 100} \\ [\text{Total number of tablets planned to receive up to Weeks 28}]$$

where total number of tablets planned to receive up to Weeks 28 = 2 × number of days the subject was during 28 weeks (the previous date of Weeks 28 visit date [for completed Week 28 subjects] / date of withdrawal date [for discontinued before Week 28 subjects] – date of initial dose of study drug +1), and total number of tablets actually received up to Weeks 28 will be calculated as:

(total number of tablets dispensed up to Weeks 28) – (total number of tablets returned up to Weeks 28) – (total number of tablets lost up to Weeks28).

\*If Weeks 28 visit date is missing but not discontinued before Day 197, then the total number of tablets planned to receive up to Weeks 28 = 2 × 196 (i.e. days from the previous date of scheduled visit at Week 28 – the date of initial dose of study drug + 1)

- Number of prior DMARD biologics, calculated as number of unique kinds of DMARD biologics prior to initial dose from following CRF page.  
[Concomitant Medication 2B -page of the CRF]  
[Biologic DMARD -page of the CRF]
- Number of prior DMARDs (including biologics), calculated as number of unique kinds of DMARD prior to initial dose from following CRF page.  
[Concomitant Medication 2B -page of the CRF]  
[Concomitant Medication(Non-Biologic DMARD) -page of the CRF]  
[Non Biologic DMARD\_MTX -page of the CRF]  
[Non Biologic DMARD except for MTX -page of the CRF]  
[Biologic DMARD -page of the CRF]
- MTX Dose at Baseline (mg/week) is defined as the dose which is taken during 6 days before “date of initial dose of study drug” up to “the initial dose of study drug”.

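### SAP 7.3.1 cuts exposure duration at visit-day numbers, so a subject who completes 52 weeks exactly on schedule (364 days) is tabulated below the top row

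*SAP*

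**What the plan says.** - **Long-term safety as a reason for the size.** SAP 4, like Protocol 7.1, adds to the power calculation that "this sample size is also needed to keep 300 subjects for 6 month period, 100 subjects for 1 year period". The same sentence goes on to say that this is for both doses and is counted across RAJ2, RAJ3 and RAJ4.
- **Length of treatment.** Protocol 2.2.1 says "the duration of treatment was set at 52 weeks to evaluate the 1-year efficacy and safety as secondary endpoints". In the Schedule of Assessments the Week 52 visit is Day 365, with a window of 7 days either side, and drug is prescribed at Weeks 0 to 48 only.
- **Duration of exposure.** SAP 6.5 defines it as date of last dose minus date of first dose, plus 1. In the same section, planned tablets for completers are counted up to "the previous date of Week 52 visit". For a subject with no recorded Week 28 visit date, the planned number is 2 × 196 tablets, explained as "days from the previous date of scheduled visit at Week 28" back to the first dose, counted inclusively.
- **Exposure table.** SAP 7.3.1 asks for descriptive statistics of duration and two sets of categories. Up to Week 12, the rows start at 1, 29, 57 and 85 days. Overall, they start at 1, 85, 197, 281 and 365 days. No row is labelled in weeks, months or years.

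**The concern.** The row limits are the visit days of Weeks 4, 8, 12, 28, 40 and 52, each equal to 7 × week + 1. A visit day is not a duration. Someone seen on Day 7x + 1 and last dosed the day before has 7x days of exposure, one day short of the limit.

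This matters most for the overall top row. Safety over 52 weeks is a stated objective, and a reader will take the row from 281 to under 365 days as people who stopped before 52 weeks. As written, that row also holds subjects who took every planned dose. Among completers, what separates it from the top row is whether the last visit was late.

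**Working it through.** **1. The plan's own sample size.** Inputs from SAP 4: "the change in mTSS at Week 28 was estimated to be 0.5 in ASP015K 150 mg group"; "the change in mTSS at Week 28 was estimated to be 2.0 in the placebo group"; "The standard deviation of the change was also estimated and set to 4.0". The difference is 2.0 − 0.5 = 1.5 with SD 4.0. A two-sided 5% t-test has power 89.92% at 150 per group and 90.11% at 151. Fisher's exact test at 151 per group has power above 99.99% (65.5% v 25%) and 99.95% (54.5% v 25%). The product over Steps 1 to 3 is 90.07%. This reproduces "at a 2-sided 5% significance level with 90% power is 151 subjects per group". Allowing for 10% drop-out, 151 / 0.90 = 167.8, so 168, against 170 planned. The size is sound. The only figure carried forward is planned completers per active arm: 170 × 0.90 = 153.

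**2. The day count.** 28 × 7 = 196, which reproduces the SAP's own figure in 6.5. By the same rule 12 × 7 = 84, 40 × 7 = 280 and 52 × 7 = 364.

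**3. Where a completer falls.** With first dose on Day 1, the Week 52 visit on Day d and last dose on Day d − 1, duration is (d − 1) − 1 + 1 = d − 1.

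| Week 52 visit | Duration (days) | Row in 7.3.1 |
|---|---|---|
| Day 358 | 357 | 281 to <365 |
| Day 364 | 363 | 281 to <365 |
| Day 365 | 364 | 281 to <365 |
| Day 366 | 365 | 365 or more |
| Day 372 | 371 | 365 or more |

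Eight of the 15 window days (358 to 365) fall below the top row and seven (366 to 372) reach it.

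**4. How many.** The documents give no distribution of visit days, so this is an assumption, shown as a range.

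- All visits on Day 365: 0 of 153 reach the top row.
- Uniform over Day 358 to 372: 7/15 = 46.7%, and 153 × 7/15 = 71.4, about 71.
- Any spread symmetric about Day 365, with share p on Day 365 itself: (1 − p)/2, which never exceeds one half.
- Extremes: 0 if every visit is on or before Day 365, 153 if every visit is later.

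**5. What a 364-day cut does.** It moves up exactly the subjects seen on Day 365. If all visits are on Day 365, the top row goes from 0 to 153. Under the uniform assumption it goes from 7/15 (71) to 8/15 (153 × 8/15 = 81.6, about 82). Completers seen on Day 358 to 364 still fall below.

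**6. The Week 12 table.** If exposure there ends the day before a Day 85 visit, it is 84 days and misses the row starting at 85. If the dose on Day 85 is counted, it is 85 days and reaches it. SAP 6.5 ends planned tablets the day before the Week 12 visit for compliance, but gives no rule for where exposure up to Week 12 stops.

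**The case against.** **The targets are pooled.** A reader might infer that the trial contradicts its own target of 100 subjects for 1 year, or would seem to miss it. The documents do not support that. The target spans three studies, completers may continue in RAJ2, and nothing says the table in 7.3.1 will be used to count it. The same applies to the 6-month target of 300. This objection stands.

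**No row is called 1 year.** Correct. The SAP also uses 365.25 days per year for yearly mTSS progression and patient-years, so a band starting at 365 days could be defended as a calendar year. That does not explain 29, 57, 85, 197 and 281, which show the same 7x + 1 pattern, and Protocol 2.2.1 treats 52 weeks as its 1-year evaluation.

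**A dose might be taken on Day 365.** Protocol 5.1.1 has visit-day doses given after assessments, and each box holds spare tablets. If that covered Week 52, duration would be 365 days and the top row would be reached. Three things point the other way: nothing is prescribed at Week 52; the windows for Weeks 4 to 48 carry a pre-dose condition that Week 52 lacks; and SAP 6.5 ends planned dosing the day before.

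**The interior overall cuts hardly matter.** This stands. Total duration is classified, so moving 85, 197 and 281 down by one reclassifies only subjects whose last dose fell exactly on Day 84, 196 or 280. They should change for consistency, not for effect.

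**The information is available elsewhere.** Partly. SAP 7.3.1 also reports descriptive statistics of duration, SAP 7.2.1 tabulates discontinuations, and patient-year rates use actual time. A reader could work out completers from these, but the categorical exposure table would still give the wrong impression.

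**Conclusion.** The point holds as a one-day boundary fault in a descriptive safety table. A subject randomised to ASP015K who takes every planned dose for 52 weeks and attends on Day 365 has 364 days of exposure and is placed in the row from 281 to under 365 days. Between 0 (all visits on Day 365) and about 71 (visits uniform over the window) of 153 planned completers per active arm would reach the top row. More would do so only if visits ran late overall.

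This rests on the last dose being the day before the Week 52 visit, which the documents favour but do not state outright, and on 10% drop-out. The matching fault in the Week 12 table is conditional on a rule that the SAP does not give.

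It would be wrong to read this as an error in the sample size or as evidence that the pooled 6-month or 1-year counts will fall short. Power, the 170 per group, the analysis sets and every test are unchanged. What is understated is 52-week exposure in this trial's own categorical table.

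**What to change.** In SAP 7.3.1, set the cut-points in completed weeks: 28, 56 and 84 days for the table up to Week 12, and 84, 196, 280 and 364 days overall. State the last day counted in the Week 12 table.

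Add a row with the number of subjects who completed Week 52 on ASP015K, by initial arm. The new cut alone still puts completers with in-window visits on Day 358 to 364 below the top row.

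If the table is also meant to show this trial's contribution to the pooled 6-month and 1-year counts in SAP 4, state the day thresholds used for each. The choice is the sponsor's, as the documents give none.

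The cost is a few lines of SAP wording and one table program, with no new data. If the SAP is not reopened, the change can be explained in the clinical study report, as SAP 1 provides.

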## 5 ANALYSIS SETS

In accordance with International Conference on Harmonization (ICH) recommendations in guidelines E3 and E9, the following analysis sets will be used for the analyses. FAS will be the primary data set for efficacy analyses.

### 5.1 Full Analysis Set (FAS)

The FAS will consist of all subjects who are randomized and receive at least one dose of the study drug. This will be the primary data set for efficacy analyses.

### 5.2 Per Protocol Set (PPS)

#### 5.2.1 PPS for Assessing ACR and DAS at Week 12 (PPS-ACR)

The PPS-ACR includes all subjects of the FAS who meet the following criteria. PPS-ACR is defined based on the data up to Week 12.

- Have no violation of inclusion criteria;
- Do not meet any exclusion criteria possibly interfering with the efficacy evaluation;
- Period of study treatment between the initiation of administration and Week 12 is 8 weeks (56 days) or longer (those who have discontinued study treatment due to the lack of efficacy will be included in PPS);
- Have treatment compliance of 75% or higher during the 12 weeks of study administration (Week 12 or at early termination before Week 12);
- Have evaluable ACR20 at the end of Week 12 (Week 12 or at early termination before Week 12);
- Have no major protocol violations after registration.

Subjects who are considered to have no impact on the efficacy evaluation at the Case Review Meeting will also be included in the PPS-ACR, if they are not satisfying these criteria.

### **5.2.2 PPS for the Assessment of the Inhibition of Joint Destruction at Week 28 (PPS-MTSS)**

The PPS-MTSS includes all subjects of the FAS who meet the following criteria. PPS-MTSS is defined based on the data up to Week 28.

- Have no violation of inclusion criteria;
- Do not meet any exclusion criteria possibly interfering with the efficacy evaluation;
- Period of study treatment between the initiation of administration and Week 28 is 8 weeks (56 days) or longer (those who have discontinued study treatment due to the lack of efficacy will be included in PPS);
- Have treatment compliance of 75% or higher during the 28 weeks of study administration (Week 28 or at early termination before Week 28)
- Have evaluable change in mTSS from baseline at the end of Week 28 (Week 28 or at early termination before Week 28)
- Have at least 1 mTSS data at baseline and from Week 12
- Have no major protocol violations after registration

Subjects who are considered to have no impact on the efficacy evaluation at the Case Review Meeting will also be included in the PPS-MTSS, if they are not satisfying these criteria.

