For each comparison, only the data for two treatment groups to be compared will be used. For the missing imputation of ACR20-CRP at Week 12/ET, Last Observation Carried Forward (LOCF) methodology will be used.

For subjects who discontinued at or before Week 28 or switched to receive ASP015K instead of placebo at Week 12 due to the lack of efficacy, mTSS at Week 28 will be extrapolated using linear extrapolation method based on the mTSS at baseline and early termination or Week 12 (before switching).

Cumulative probability plot for the change from baseline in mTSS score at Week 28/ET will be created.

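### For placebo subjects switched at Week 12, PPS-MTSS membership is judged on data to Week 28 but their analysed mTSS uses only pre-switch films, so some can be wrongly kept or dropped in that one sensitivity analysis

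*SAP*

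**What the plan says.** **Membership.** SAP 5.2.2 (and Protocol 7.2.2.2, in the same terms) says that "PPS-MTSS is defined based on the data up to Week 28". Among its conditions are "Have treatment compliance of 75% or higher during the 28 weeks of study administration" and "Have no major protocol violations after registration". Neither has an exception for placebo subjects who change treatment. A further condition is "Period of study treatment between the initiation of administration and Week 28 is 8 weeks (56 days) or longer". Section 5.2.2 closes by letting the Case Review Meeting include subjects who fail a criterion but are judged not to affect the efficacy evaluation.

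**Compliance formula.** SAP 6.5 puts "Total number of tablets actually received up to Weeks 28" in the numerator. The denominator is two tablets times "number of days the subject was during 28 weeks", counted to the day before the Week 28 visit or to withdrawal. Placebo and ASP015K tablets are added together, with no cut at the switch.

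**Outcome.** For placebo subjects who "switched to receive ASP015K instead of placebo at Week 12 due to the lack of efficacy, mTSS at Week 28 will be extrapolated" (SAP 7.4.1.1), SAP 7.11.1 confirms that the extrapolation uses baseline and the film before switching. SAP 7.4.1.2 applies the same linear extrapolation in PPS-MTSS.

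**The Week 12 set.** PPS-ACR (SAP 5.2.1) has the matching shorter condition: "Have treatment compliance of 75% or higher during the 12 weeks of study administration".

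**The concern.** A per-protocol set should select on conduct during the period that produces the analysed value. For Week 12 switchers, the value is fixed before the switch, but selection continues for 16 more weeks on ASP015K. Two kinds of error become possible. Poor adherence to placebo can be masked by good adherence to ASP015K. Good adherence to placebo can be overridden by missed doses or a major violation on ASP015K.

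The mismatch arises only in the placebo arm. An ASP015K subject with the same poor Week 12 response stays on the assigned dose. If that subject completes to Week 28, the Week 28 film is analysed, so the 28-week window fits.

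Elsewhere the SAP does cut at the switch: in the mTSS imputation (7.11.1), yearly mTSS progression (6.1.2.2), attribution of adverse events (6.2) and the Week 12/ET efficacy values (7.11.4). PPS-MTSS membership lacks the matching cut. What is at stake is how well the PPS-MTSS repeat of the mTSS tests does its stated job in SAP 7.4, which is to check the robustness of the FAS result.

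**Working it through.** **Inputs**
- Planned days to Week 28: 196 (Day 1 to the day before Day 197). SAP 6.5 uses 2 × 196 when the Week 28 visit date is missing, so the plan's own denominator of 392 tablets is reproduced.
- Planned days before the switch: 84 (Day 1 to the day before Day 85), or 168 tablets.
- Days after the switch: 196 − 84 = 112, or 224 tablets.
- Cut-off: 75%.

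**Share of the window after the analysed data:** 112/196 = 57.1%.

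**28-week compliance of a switcher:** (84 × pre + 112 × post)/196, which is 0.43 × pre + 0.57 × post. Passing needs 0.75 × 196 = 147 dosing days.
- Wrongly kept, at the limit: with full post-switch compliance, 147 − 112 = 35 of 84 placebo days are enough, i.e. 41.7%.
- Wrongly dropped, at the limit: with full pre-switch compliance, 147 − 84 = 63 of 112 days are needed, so a subject fails below 56.3%.

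**Effect of the ±7-day visit windows.** With 77 to 91 days before the switch and 189 to 203 days in total, the post-switch share runs from 52% to 62%, the first limit from 34% to 48%, and the second from 52% to 60%.

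**Examples at nominal visit days**

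| Pre-switch | Post-switch | 28-week figure | Current status | Status on the analysed window |
|---|---|---|---|---|
| 50% | 95% | 75.7% | passes | fails |
| 66.7% (56/84, one 28-day interruption) | 100% | (56 + 112)/196 = 85.7% | passes | fails |
| 100% | 55% | 74.3% | fails | passes |

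The second row uses a gap that Protocol 3.4.1 permits. SAP 6.5 does not deduct interruption days from the planned tablets. That subject fails the PPS-ACR compliance criterion on the same 12 weeks that supply the only on-treatment film used in PPS-MTSS.

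**How many subjects come under the rule.** The documents give no switch rate. A switcher has less than 20% joint-count improvement and so cannot be an observed ACR20 responder. At the planning placebo response of 25% (SAP 4), the ceiling is 0.75 × 170 = 127.5, i.e. about 127 subjects. With an assumed switch rate of 30% to 60%, the number is 51 to 102. These figures count subjects judged by the rule, not subjects misclassified.

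**56-day criterion.** A Week 12 switcher has normally had 84 days of treatment before the switch, so this condition is unaffected.

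**The case against.** **The Case Review Meeting can correct membership.** SAP 5.2.2 allows it to restore a subject whose lapse has no impact on efficacy, and a lapse after the switch fits that description well. Protocol 7.2 gives it the final judgment on both inclusion and exclusion. This stands as a partial safeguard. It is discretionary, however, and Protocol 7.9 places the meeting before code breaking. The switch is blinded, so the meeting cannot tell a switched placebo subject, whose later conduct is irrelevant to the analysed value, from an ASP015K subject with the same poor response, whose later conduct matters.

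**The limits are extreme.** Being dropped on compliance after full placebo adherence takes at least 50 missed doses of 112. That is one full 28-day interruption plus 22 more days, more than three maximum 7-day suspensions. Protocol 3.4.1 forces withdrawal at a second interruption within 16 weeks, and 3.4 makes judged non-compliance a reason to discontinue. On withdrawal the denominator stops: with full placebo adherence and no later doses, 84/(84 + d) is not below 0.75 until d exceeds 28 days. At the other limit, 49 of 84 placebo doses must be missed. Protocol 2.2.2 also reports excellent adherence in the Phase IIb study. All this stands as evidence that such cases are probably rare. It does not cover the violation criterion, where one major violation after the switch is enough.

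**The switch is part of the placebo regimen, so adherence to Week 28 is a coherent definition.** It would be if the Week 28 film were analysed for these subjects. The plan sets that film aside and extrapolates.

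**Changing the rule would treat the arms differently.** The criterion would then use different calendar windows, but only because the analysed data already do. One principle would apply to everyone: the membership window equals the data window. What stands is that the rule depends on treatment assignment and must be made workable under the blind.

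**Conclusion.** The mismatch is real: the PPS-MTSS rule for Week 12 placebo switchers covers 16 weeks after their analysed data end, 57% of the window (52% to 62% across visit windows). Misclassification is possible in both directions, within the limits of 41.7% and 56.3%.

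A reader might infer that the wrong placebo subjects will in fact be kept or dropped, or that the mTSS conclusion is compromised. The documents support neither. An error on compliance needs pre- and post-switch compliance to fall on opposite sides of the threshold in the way shown; otherwise it needs a major violation that occurs only after the switch. The number of such subjects cannot be computed from the documents and is probably small.

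Interpretation rests on the FAS (SAP 7.4), and PPS-MTSS is one of five mTSS sensitivity analyses (SAP 7.4.1.2). The FAS primary test, alpha and sample size are unaffected. The calculation assumes nominal visit days and two tablets a day. The switch rates are assumptions.

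**What to change.** Add to SAP 5.2.2, before code break and as a clarification of Protocol 7.2.2.2: for placebo subjects switched to ASP015K at Week 12, the compliance and major-violation criteria are assessed on data before the first ASP015K dose, using the compliance variable up to Week 12 already defined in SAP 6.5. Keep the 28-week criteria for all other subjects, and leave the 56-day criterion unchanged.

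To protect the blind, determine and freeze both the Week 12 and the Week 28 status before code break for every subject, in any arm, with less than 20% improvement in TJC and SJC at Week 12. After unblinding, a program applies the Week 12 status to switched placebo subjects and the Week 28 status to the rest.

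The cost is a short SAP addition, a small amount of programming, and blinded review of two statuses instead of one for the subjects concerned. No new data are needed.
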